1. INTRODUCTION

1.1. Understanding ureteral obstruction

Ureteral obstruction can be caused by stones, infectious scars, trauma, congenital abnormalities, surgery, and also by malignant diseases¹. The prevalence of malignant ureteral obstruction ranges from 21% to 82% in case series reported in the literature^{1, (2)}.

It occurs when there is invasion or extrinsic compression of the ureter by the tumor mass or by metastatic lymph nodes present in the pelvis, around the ureters or in the retroperitoneum^{1, 3(,) (4)}, causing partial or total occlusion of this ureter, which can result in acute kidney injury, the mortality of which is between 53% and 93% in severe cancer patients⁵. Malignant ureteral obstruction is responsible for around 7% of all causes of acute kidney injury in cancer patients⁽⁶⁾.

The main types of neoplasms responsible for ureteral obstruction are prostate cancer⁷⁻¹⁰, bladder cancer⁷⁻⁹, cervical cancer^{7, 9-11}, ovarian cancer^{7(,) (10)(,) (11)} and colon-rectal cancer⁸⁻¹¹ because they are anatomically close to the urinary tract.

Generally, malignant ureteral obstruction is caused by an advanced or progressing neoplastic disease, commonly associated with metastases, bringing with it a worse prognosis¹². However, if clearance is not achieved, the threat to life is imminent^{2, 7, (13)}.

1.2. Clearing the urinary tract

Urinary tract clearance is the treatment indicated to stop the high pressure inside the urinary tract and restore renal function, ensuring the continuity of cancer treatment or relieving uremic symptoms in more advanced diseases^{2, (13)}.

The techniques and procedures to be used for such clearance include percutaneous nephrostomy, the passage of ureteral catheters (double-J catheter, internal-external catheter or metal catheter) and ureteral shunts (nephrocutaneous *bypass*, cutaneous ureterostomy, transuretero-ureterostomy or Bricker ileal conduit), with these ureteral shunts being the last choices in palliative care as they are more invasive

procedures causing greater associated morbidity for patients with advanced neoplastic disease ⁽¹²⁾.

The choice of method will depend on the stage of the disease, the patient's clinical conditions and the pelvic anatomical alteration caused by the neoplasm, always considering the least invasive technique with the least interference in the local anatomy, such as the passage of the double-J catheter ^{14, (15)}.

However, percutaneous nephrostomy assumes its importance if the ascension of any type of catheter through the urinary tract is made impossible by the presence of a bladder tumor, local extrinsic compressions and even fistulas and hemorrhages ^{7, 12, (15)}.

1.3. About percutaneous nephrostomy

It was first described in 1955 as the insertion of a plastic tube into the renal pelvis (the funnel-shaped structure that drains the urine produced by the kidney into the adjoining ureter) after X-rays with contrast medium to draw this pelvis (antegrade pyelography) in patients with ureteral obstructions and undergoing urine drainage by lumbar puncture ¹⁶. In 1974, ultrasound was used to guide this procedure, making it safer ⁽¹⁷⁾.

The main indication is for urinary tract clearance of benign or malignant origin, with or without infection (72% to 97% of all indications). It can also be used to control and treat ureteral fistulas and hemorrhagic cystitis (1% to 34% of all indications) and for diagnostic tests and access for therapeutic interventions (2% to 50% of all indications) ^{18(,) (19)}. Relative contraindications include severe uncontrolled coagulopathies (risks of renal hemorrhage) and terminal illness / imminent death, as it becomes an unnecessary and futile procedure ⁽¹⁸⁾.

Percutaneous nephrostomy catheters can be used until the obstruction of the urinary tract is resolved by surgery, chemotherapy or radiotherapy, preventing kidney damage and allowing recovery of kidney function. They can also be used as a permanent palliative option in patients with advanced and/or untreatable neoplastic disease ⁽¹⁹⁾.

Success rates range from 84% to 99%, being lower in undilated urinary collecting systems, complex calculous disease and coralliform calculi, but with rates of 96% to 100% in obstructed urinary tracts with or without calculi ²⁰. Even so, percutaneous nephrostomy is not a complication-free procedure.

1.4. Complications related to percutaneous nephrostomy

The International Society of Interventional Radiology classifies complications based on results into minor and major complications (Appendix I) ⁽²¹⁾.

The complications inherent in this procedure occur in around 10% of patients with both benign and malignant diseases ¹⁸. However, the figures can reach 29% (when only ureteral lithiasis is studied) ⁽²²⁾.

1.4.1. Minor complications

There are reports of a 3% to 28% prevalence of minor complications ^{23, 24}, with spontaneously resolving hematuria accounting for 13.2% to 18.9% ^{22(,)(23)(,)(25)}; pain occurs in 25% of cases ²² and catheter migration ranges from 12% to 17% ^{10) .. (22)}

1.4.2. Major complications

One study found no major complications (death, hematuria requiring surgical management or blood transfusion, vascular laceration, pseudoaneurysm or arteriovenous fistula, infection requiring surgical management, sepsis or puncture of adjacent organs such as colon, spleen or lung) ²⁴. However, a non-systematic review reports the following rates of these complications ⁽¹⁸⁾:

- a) Individual complications that resulted in unexpected transfer to an intensive care unit, emergency surgery or prolonged hospital stay: 1% to 7%;
- b) Pleural complications (pneumothorax, empyema, hydrothorax, hemothorax): 0.1% to 0.6%;
- c) Intestinal perforation: 0.2% to 0.5%;
- d) Vascular injury requiring embolization or nephrectomy: 0.1% to 1%;
- e) Bleeding requiring blood transfusion: 1% to 4%;
- f) Septic shock due to pyelonephritis: 7% to 9%;
- g) Septic shock (fever, chills with hypotension, requiring a higher level of care): 1% to 10%.

1.4.3. Infectious complications

Even though the aforementioned review showed rates of pyelonephritis and septic shock related to percutaneous nephrostomy of up to 10%, the proportions of infectious complications can vary in the literature:

- a) without evidence of urinary infections ^{23, (24)} ;
- b) 8.5% of catheter insertion site infections ⁽²⁵⁾ ;
- c) 10.3% of intra-renal or peri-renal abscesses ⁽²⁵⁾ ;
- d) 3.7% to 15% of febrile episodes ^{11, 14, (26)} ;
- e) 11.6% to 38.1% urinary tract infection ^{7, 9(,) (10)(,) (19)} ;
- f) 7% of infections related to percutaneous nephrostomy ⁽²⁷⁾ ;
- g) 3.8% to 19% pyelonephritis ^{3, 14} and
- h) 9% to 50% septicemia ^{9, (22)} .

In studies of patients undergoing percutaneous nephrostomy for malignant ureteral obstruction alone, catheter-related urinary infection ranged from 3.8% to 38.1% ^{3, 7(,) (9)(,) (10)(,) (14)(,) (19)(,) (25)} .

These disparate values exist because there is no robust clinical evidence on the best way to diagnose nephrostomy catheter-related urinary tract infection, especially in cancer patients, i.e. the definitions used in the studies are methodologically varied ⁽¹⁹⁾ .

Of the proportions of urinary infection cited above, seven studies do not methodologically define nephrostomy catheter-related urinary tract infection ^{7, 9(,) (10)(,) (23-25)} . One study defines urinary infection as fever and flank pain accompanied by bacteriuria or pyuria with no other focus, but does not mention uroculture and time after procedure ¹⁴ . Another study defines an infectious complication only as fever (temperature greater than 38°C) within 30 days of follow-up ²⁶ . A third study defines temperature as less than 36°C or greater than 38°C, associated with a white blood cell count greater than 10,000 cells/mL, positive uroculture and blood culture ⁽²⁷⁾ .

Bahu *et al.* defined pyelonephritis as at least 1 sign or symptom (fever greater than 38°C, pain on costovertebral percussion and/or flank pain) associated with uroculture with growth of no more than two species of microorganisms greater than or equal to 10⁵ CFU/ml at 90-day follow-up after the procedure ³ . Szvalb *et al.* define infection related to percutaneous nephrostomy as any clinical symptom (fever, chills, pain on costovertebral percussion, hypotension and/or cellulitis at the catheter entry site) not explained by another diagnosis associated with uroculture with bacterial growth greater than or equal to 10⁴ CFU/ml at a follow-up of 100 days after the procedure ¹⁹ . The last study mentioned only signs of sepsis: chills and fever at the time of the procedure with or without hypotension ⁽²²⁾ .

Inaccurate diagnosis can lead to inadequate treatment, resulting in irrational use of antimicrobials and, consequently, future infections with multi-resistant bacteria. This is a cause for concern, as it aggravates the clinical condition of patients with neoplasms who are already immunocompromised, both because of the tumor and the cancer treatment itself.

1.5. Is it possible to avoid a urinary tract infection related to a percutaneous nephrostomy catheter?

At the same time as there is no consensus on the definition of nephrostomy-related urinary tract infection, there is also no consensus on its prophylaxis. In order to assess it, it is necessary to take into account the formation of a biofilm of microorganisms on the catheter (perhaps this is the most important factor) and the use of antibiotics.

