1.5.1. The Biofilm Question

Colonization of the nephrostomy catheter occurs as soon as it is passed into the patient¹⁹, leading to the development of a three-dimensional biofilm²⁸, containing a high concentration of microorganisms which are under relative protection from both the immune system and antimicrobials, associated with intraluminal fouling can lead to catheter dysfunction and clinical infection, from pyelonephritis and abscesses to bacteremia and septic shock^{18, (29)}.

Biofilm is therefore a reservoir of microorganisms which can perpetuate an episode of infection or even facilitate a new one¹⁹. Therefore, the best way to prevent infection is to use the nephrostomy catheter for as short a time as possible. However, if patients need this catheter for a long period of time, one way of mitigating catheter-related urinary tract infection would be to change the catheter after a period of use.

The time used to change the catheter varies according to expert opinion and institutional protocols, ranging from 10 weeks³⁰ to 3 months³. One study proposed a model to define the best time to change, associated with fewer complications, better patient compliance and lower costs, concluding that changes could be made every 60 days⁽²⁰⁾.

In situations where urinary tract infections related to the nephrostomy catheter recur, a retrospective study suggests that the catheter should be changed up to four

(4) days after starting the appropriate antimicrobial to treat the current infection and maintain this antimicrobial for 14 days of treatment ⁽¹⁹⁾.

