3.2. Secondary

- Describe the frequency of urinary tract infection related to the percutaneous nephrostomy catheter that occurs between catheter changes (not related to the procedure, but possibly to colonization of the catheter);
- To describe and compare the results of the urocultures involved in the study, as well as their sensitivity to the antibiotics used;
- Describe the main signs and symptoms involved in urinary tract infection related to the procedure and the nephrostomy catheter;

- Assess the severity of urinary tract infections according to the type of treatment and the need for hospitalization.
- To determine the risk factors for urinary tract infection related to the passage and subsequent changes of nephrostomy catheters.
- Describe the rates of urinary infections and associated germs according to the time of nephrostomy passage, first passage or catheter change.
- Report whether these catheters were changed when the urinary tract infection occurred and on which day after the urinary tract infection was diagnosed.

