4.10.3. Procedure for changing the catheter

Catheter changes take place electively approximately every 90 days after the previous procedure (first pass or previous catheter change), scheduled during outpatient follow-up. However, this change can happen earlier than planned due to situations such as catheter obstruction and migration, or even catheter-related urinary tract infection.

This group will be made up of patients undergoing percutaneous nephrostomy catheter exchange and will study the use of empirical or targeted antibiotic prophylaxis documented in medical records to be reviewed at the two hospitals.

The Jales Cancer Hospital will study targeted antibiotic prophylaxis, which consists of collecting the following laboratory tests around 7 days before the procedure

to change the nephrostomy catheter(s) to guide the antibiotic to be used for prophylaxis: serum creatinine and urea levels, urine samples for tests such as urine summary (or type I urine) and uroculture with antibiogram. If the tests are not carried out prior to the procedure or if the uroculture does not show a specific bacterial agent, the procedure will be studied according to empirical antibiotic prophylaxis.

The Hospital de Câncer de Barretos will study the empirical antibiotic prophylaxis carried out according to daily clinical practice, recorded in the medical records to be reviewed of patients undergoing percutaneous nephrostomy catheter exchange.

The proportion of urinary tract infections that developed within 7 days of the procedure will be studied. A procedure-related urinary tract infection is considered to be any report in the medical record of clinical signs and symptoms associated with uroculture results (see definition in item 4.10.4.) and the location of the respective treatment will be documented: outpatient, inpatient or intensive care unit (ICU).

It will be documented whether there is evidence reported in medical records of urinary tract infections or the presence of bladder fistulas prior to the procedure.

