4.10.5. Study variables

The study variables will make up the research instrument used to collect the data (see Appendix II).

Sociodemographic and clinical variables: gender, color, age, weight, height, underlying neoplastic disease, performance status and number of organs affected by metastases. Presence of fever, low back pain, pain at the wrist-percussion of the lumbar region, pain in the hypogastrium, dysuria and polyuria and presence of cloudy urine.

Radiological data: degree of urinary tract obstruction.

Dates of diagnosis of the underlying neoplasm and diagnosis of malignant ureteral obstruction.

Laboratory data: blood count, creatinine, urea, type I urine, uroculture and antibiogram.

Antibiotics: for the prophylaxis or treatment of urinary tract infection and sensitivity of the first antibiotic used for prophylaxis and/or treatment.

Colonizing and infecting agents and their classification in terms of multidrug-resistant organisms

Period of use of the catheter(s); removal of the catheter(s); other complications, such as mobility of the catheter(s) and/or obstructions.

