4.12. Statistical Analysis

The data will initially be tabulated in an electronic spreadsheet in REDCap and for the statistical analysis, only the research team's statistician will download the data into the statistical program (SPSS). The study population will be characterized using descriptive statistics, using the mean, standard deviation, minimum, maximum and quartiles for quantitative variables and frequency tables for qualitative variables.

The database will be made up of patient information and procedure information, but with a unique identifier for each patient, allowing information to be linked between them.

For the purposes of this study, nephrostomy procedures will be considered independent. The procedures will be separated into first pass and catheter changes. In the first passage, procedures with antibiotic prophylaxis and without antibiotic prophylaxis will be studied. In catheter changes, procedures with empirical antibiotic prophylaxis and with targeted antibiotic prophylaxis will be studied. The types of procedures and the other characteristics of the procedures will be associated with the occurrence of urinary tract infection using the Chi-square test or Fisher's exact test, depending on the expected values in the contingency table. The multiple analysis will be carried out using Logistic Regression with multiple variables. To this end, only the variables with a p-value of less than 0.20 in the univariate analysis will be selected for the model.

The significance level will be 5%, two-sided, for all statistical analyses, which will be carried out using the SPSS v21 program.

Part II - Systematic Review and Meta-Analysis

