Barretos Cancer Hospital

Antibiotic prophylaxis in urinary tract clearance by percutaneous nephrostomy and catheter changes in patients with malignant ureteral obstruction: Retrospective cohort study and systematic review with meta-analysis

NCT Number: NCT06801405

Unique Protocol Id: 44395921. 4.0000.5437

Area of Concentration: Oncology

Researcher: [name]

Supervisor: [name]. [name]

Barretos-SP, January 11, 2021

Statistical Analysis Plan

Study variables

The study variables make up the research instrument used for data collection.

Sociodemographic and clinical variables: gender, color, age, weight, height, underlying neoplastic disease, performance status and number of organs affected by metastases. Presence of fever, low back pain, pain at the wrist-percussion of the lumbar region, pain in the hypogastrium, dysuria and polyuria, presence of cloudy urine and organ dysfunction. The presence of leukocyturia (elevated white blood cell count on urine sediment examination), leukocytosis (elevated white blood cell count on blood count examination) and positive uroculture will also be checked if they have been used as a therapeutic decision for urinary infection.

Radiological data: degree of urinary tract obstruction.

Dates of diagnosis of underlying neoplasm and diagnosis of malignant ureteral obstruction.

Laboratory data: blood count, creatinine, urea, type I urine, uroculture and antibiogram.

Antibiotics: for the prophylaxis or treatment of urinary tract infection and sensitivity of the first antibiotic used for prophylaxis and/or treatment.

Colonizing and infecting agents and their classification in terms of multidrug-resistant organisms

Period of use of catheter(s); removal of catheter(s); other complications, such as mobility of catheter(s) and/or obstructions.

Data Storage Plan

The data was stored on the REDCap platform, which is among the best platforms for collecting, managing and storing data for research and multi-institutional studies. It complies with the American laws on the protection of patient data, the Health Insurance Portability and Accountability Act (HIPAA). In addition to secure data storage and management, research data is stored on the institution's own server.

Statistical analysis

The data was extracted from the REDCap platform into the SPSS statistical program. The study population was characterized using descriptive statistics, using the mean,

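### Catheter age at a change is adjusted for in the guided-versus-empirical comparison only if it passes a p<0.20 screen, so an imbalance between the groups could bias the result in either direction

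*Protocol*

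**What the plan says.** Section 1.5 of the protocol sets the premise for assessing prophylaxis: "it is necessary to take into account the formation of a biofilm of microorganisms on the catheter (perhaps this is the most important factor". Section 1.5.1 ties this to time: "the best way to prevent infection is to use the nephrostomy catheter for as short a time as possible".

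Section 4.10.3 gives one schedule: "Catheter changes take place electively approximately every 90 days after the previous procedure". It then allows earlier changes for obstruction, migration or catheter-related infection. Guided prophylaxis is studied at Jales and empirical prophylaxis at Barretos. A Jales change with no prior tests, or whose culture shows no specific agent, is counted as empirical.

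Catheter duration is collected. Protocol section 4.10.5 lists "Period of use of the catheter(s); removal of the catheter(s); other complications, such as mobility of the catheter(s) and/or obstructions", and the SAP's list of study variables has "Period of use of catheter(s); removal of catheter(s); other complications, such as mobility of catheter(s) and/or obstructions".

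There is also a route to analysis. Section 3.2 includes the objective "To determine the risk factors for urinary tract infection related to the passage and subsequent changes of nephrostomy catheters". Under section 4.12, "the other characteristics of the procedures will be associated with the occurrence of urinary tract infection" by chi-square or Fisher's exact test, and variables with a univariate p-value below 0.20 go into a multiple logistic regression. The SAP has the same threshold, applied to simple logistic regression. Neither document names a covariate that stays in regardless of the screen, and neither specifies a table of catheter age by prophylaxis group.

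**The concern.** At a change, the biofilm that is disturbed sits on the catheter being removed. If that catheter's age affects the risk of UTI in the next 7 days, and if guided and empirical changes differ in mean catheter age, the crude comparison attributes the age difference to the type of prophylaxis.

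The planned safeguard is a screen on the outcome association. Confounding needs two links, one from catheter age to UTI and one from catheter age to group. The screen looks only at the first, with limited power, and says nothing about the second. A covariate that is strongly unbalanced but only moderately predictive can be dropped. As written, the rule exempts no variable, the prophylaxis group included, so an adjusted guided-versus-empirical estimate is not guaranteed either.

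At stake is the second of the two questions the protocol poses at the end of its introduction: whether culture-guided prophylaxis is better than empirical prophylaxis at catheter changes.

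**Working it through.** **1. The plan's own figures.** Section 4.9 gives 372 first passages and 358 changes: 372 + 358 = 730, as stated. The documents give no exchange interval by group and no effect of catheter age on UTI, so there is no plan figure for the bias. Steps 3 and 4 rest on assumptions.

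**2. Can catheter age differ by group?** Three features of section 4.10.3 taken together allow it.
- Group largely follows hospital.
- Some changes happen before about 90 days.
- Guided status needs a culture taken about 7 days beforehand. An unplanned early change may well lack one, and at Jales it then counts as empirical.

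The third feature would put younger catheters in the empirical group. Those changes may also be prompted by obstruction or infection, which could raise risk by another path. The direction of the net bias cannot be read from the documents.

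**3. Size by formula.** Assume that prophylaxis type has no effect and that the odds of UTI multiply by a fixed factor per 30 days of catheter age. If guided catheters are younger on average by d days, then approximately

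apparent OR = (OR per 30 days)^(−d/30).

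| Assumed OR per 30 days | d = 10 days | d = 30 days | Reversed imbalance (10; 30 days) |
|---|---|---|---|
| 1.2 | 0.94 | 0.83 | 1.06; 1.20 |
| 1.5 | 0.87 | 0.67 | 1.14; 1.50 |
| 2.0 | 0.79 | 0.50 | 1.26; 2.00 |

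For example, 1.2^(−10/30) = 0.94 and 2.0^(−30/30) = 0.50.

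**4. Does the screen protect the comparison?** A simulation used 358 changes, half of them guided, catheter age with mean 75 and SD 30 days, an overall UTI rate of 11.4% (the earlier cohort's rate after changes, section 1.5.2.3), no prophylaxis effect, and younger guided catheters. Each scenario had 3,000 runs. The screen was a score test at p<0.20, and the group comparison was a two-sided chi-square test at 5%.

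| OR per 30 days | d (days) | Apparent OR | Age fails the screen | Crude test p<0.05 |
|---|---|---|---|---|
| 1.2 | 15 | 0.91 | 55% | 6% |
| 1.2 | 30 | 0.84 | 50% | 8% |
| 1.5 | 15 | 0.82 | 12% | 9% |
| 1.5 | 30 | 0.67 | 7% | 23% |
| 2.0 | 15 | 0.72 | 0.1% | 16% |
| 2.0 | 30 | 0.52 | 0.2% | 49% |

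With no age difference, the screen dropped age in 58%, 14% and 0.2% of runs for the three gradients, and the crude test stayed near its nominal 5%. The screen therefore usually catches the gradients that do most damage and is close to a coin toss for the weak one. The last column concerns the crude test, which stays crude whatever the screen does.

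**5. Events available for adjustment.** Applying the earlier cohort's guided and empirical rates (6.4% and 14.8%, section 1.5.2.3) to all 358 changes gives 0.064 × 358 = 22.9 and 0.148 × 358 = 53.0, so about 23 to 53 events. The true number may be lower if some of the 358 had no prophylaxis and fall outside the comparison.

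**The case against.** The strongest answer is that the plan already deals with catheter duration. It is a listed variable in both documents, procedure characteristics are tested against UTI, risk factors at changes are a stated objective, and the logistic model is open to it. A reader might infer that catheter age has no place in the analysis or goes untested. The documents do not support that. What stands is narrower: its place in the adjusted comparison is conditional on a p-value.

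Second, the screen handles the worst cases. That stands for gradients of 2.0 and mostly for 1.5, provided the recorded variable is the removed catheter's age. The visible text does not say whether period of use means the removed catheter, the new one or total time. Section 4.10.5 points to Appendix II, which is not in the supplied text and may settle this, so the plan cannot be faulted for leaving it undefined.

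Third, a reader might infer that the two hospitals schedule changes differently. Section 4.10.3 gives a single interval before it separates them. The variation in timing cited in section 1.5.1 comes from the literature, not from these sites.

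Fourth, no passage says that 7-day UTI after a change rises with the removed catheter's age. Section 1.5.1 speaks of infection during catheter use, which section 4.10.1 defines separately from procedure-related infection. The gradient is an assumption, and the objection is right on that.

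Fifth, section 4.7 excludes procedures done while antibiotics are being given to treat a UTI, so some infection-prompted early changes will drop out. Changes for obstruction or migration remain.

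**Conclusion.** The point holds as a refinement of covariate selection for the comparison at catheter changes. The protocol calls biofilm possibly the leading factor in assessing prophylaxis, and section 4.10.3 makes unequal catheter age plausible. Yet the comparison is a crude test, and adjustment depends on a screen that ignores group imbalance.

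The size is unknown. Under the assumed gradients (1.2 to 2.0 per 30 days) and differences (10 to 30 days), the spurious odds ratio lies between 0.94 and 0.50, or between 1.06 and 2.0 in the other direction. It could mimic a benefit of guided prophylaxis or hide one.

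The earlier cohort's 6.4% versus 14.8% is an odds ratio of (0.064/0.936)/(0.148/0.852) = 0.39. A reader might infer that catheter age explains part of it. Nothing in the documents supports that, since they report no catheter ages for that cohort. The figure serves only as a scale against which the assumed bias would not be negligible.

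**What to change.** In protocol section 4.12 and the SAP:

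1. For each catheter change, define the age of the removed catheter as the date of this change minus the date of the previous procedure on that catheter, matched by side. State how changes with no recorded previous date are handled.
2. Tabulate this age, and whether the change was planned or unplanned and why, by prophylaxis group.
3. Keep prophylaxis group and catheter age in the guided-versus-empirical logistic model whatever their univariate p-values, with age as a linear term or a simple spline. Report the adjusted estimate beside the crude test.
4. State that the newly placed catheter's period of use is not a covariate for the 7-day outcome. It is known only afterwards, and because infection can prompt an early change, a UTI could itself shorten it.

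The SAP is written in the past tense. If the analysis is complete, report this as a labelled additional analysis.

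The cost is one or two degrees of freedom for catheter age against an assumed 23 to 53 events. The 7-day window already requires procedure dates, but records are linked by patient, so matching by side may mean returning to some charts. Because age is tied to the reason for change, residual confounding by planned versus unplanned change may remain, which is why item 2 asks for both.
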